6.2.2 Subsequent Visits during Observation Period

Subsequent visits will occur at the treating clinician's typical schedule. On each subsequent visit during the Observation Period, the following data, if available, will be collected:

- 1. Complete physical examination (including weight, height, and BSA).
- 2. Evaluation of performance status using ECOG/WHO PS score.
- 3. Safety assessment (all AEs including ADRs and SADRs).
- 4. Imaging procedures and results of imaging response evaluations will be collected, if they are available, during each cycle of the Observation Period of the study. Symptomatic response will also be collected.
- 5. Laboratory tests will be collected when available and based on the treating clinician's usual practice procedures. When available, those laboratory tests associated with ADRs and SADRs will be collected.
- 6. Data on trabectedin + PLD treatment administration.

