10.4.4 Analysis of Secondary Endpoints

Response

Response rate will be summarized. Response is defined as a best tumor response of complete or partial response as reported by the investigator. Patients without an assessment of disease response will be treated as non-responders. Descriptive statistics will be provided for best overall tumor response and response rate (CR + PR) and two-sided exact binomial 95% confidence intervals will be presented.

Disease Control

It is defined as a best tumor response assessment of CR, PR, or SD. Patients without a post-baseline tumor disease assessment will be considered to not have disease control. The disease control rate will be presented along with two-sided exact binomial 95% confidence intervals.

Overall Survival

OS will be descriptively analyzed as done for the primary endpoint PFS.

ECOG

ECOG/WHO performance status scores will be summarized at baseline, worst/best scores under treatment, and scores at end of treatment. The change in scores from baseline to best/worst and end of treatment scores will also be summarized presenting categories: <0 (indicating an improvement), 0-2, >2-4, and >4 (indicating worst deterioration).

Treatment Exposure

Trabectedin and PLD administration history will be summarized presenting the number of previous cycles received prior to IC. Descriptive statistics will be calculated for total number of cycles started, administration setting (inpatient/ outpatient), administered dose per infusion (mg), cycle duration (days), and treatment duration. Cumulative dose administered, dose intensity (mg) / week, relative weekly dose intensity (%), and total dose administered (mg) per cycles will also be presented. The number and percentage of patients with modifications (including dose missed, reductions, dose delays, or doses withheld) from the investigator reported schedule will be summarized by type of dose modification and

reason for the dose modification. The number of dose missed/reductions/interruptions/delays per patient will also be summarized.

Subsequent Anti-Cancer Treatment

Exposure to subsequent anticancer drugs will be described. Time from last dose of trabectedin, type of therapy, setting (single, combo), number of cycles, and best response will be described by regimen number, including number and percentage of patients in each regimen.

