2. OBJECTIVES

Primary Objective

To assess the progression-free survival (PFS) according to investigator criteria in relapsed ovarian cancer patients treated with trabectedin + pegylated liposomal doxorubicin (PLD) according to standard local clinical practice following approved Summary of Product Characteristics (SmPC) indication and dose, overall and by previous usage of antiangiogenic drug.

Secondary Objectives

The secondary objectives (overall and by previous usage of antiangiogenic drug) will be to:

1. Determine the response rates (complete response [CR] + partial response [PR]), and disease control rate (DCR; CR + PR + stable disease [SD])
2. Determine overall survival (OS)
3. Determine evolution of the patient's performance status (PS)
4. Evaluate treatment duration and number of cycles, treatment exposure, and time to next treatment

5. Evaluate the safety of the combination of trabectedin + PLD

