3. STUDY OVERVIEW

3.1 Study Design

This is a non-interventional, prospective, multicenter study including at least 300 patients from approximately 70 sites from Germany, Italy, Spain, France, and Belgium, with platinum-sensitive relapsed ovarian cancer for whom trabectedin + PLD is administered according to standard local clinical practice following approved SmPC indication and dose. There is no involvement with any treatment decisions for the patients included in the study.

To be enrolled in this study, the patients must meet all inclusion criteria and have none of the exclusion criteria. The reason(s) for not enrolling a patient in the study (patient declined, no reply, patient not fulfilling the selection criteria) are recorded in a patient qualification log at each site. This enables subsequent assessment of potential selection bias necessary for quality assurance of the data collected.

The study will begin with the enrollment of the first patient. The individual patient study duration will be up to 13 months (12-month Observation Period + 1-month Follow-up Period). Patients treated during the entire observation period will have a visit at month 12 and a follow up visit 1 month after. Patients ending treatment before the end of the 12 months observation period will, in addition to the 1 month after follow up visit, have an additional visit at month 12.

Trabectedin is administered every 3 weeks as a 3-hour infusion at a dose of 1.1 mg/m², immediately after PLD at 30 mg/m². There is no predefined limit as to the number of cycles of treatment with trabectedin. Treatment may continue as long as the treating physician feels there is benefit, even in the presence of apparent progression of disease.

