9.4.4 Analyses of Other Endpoints

ECOG

ECOG/WHO performance status scores will be summarized at baseline, worst/best scores under treatment, and scores at end of treatment. The change in scores from baseline to best/worst and end of treatment scores will also be summarized presenting categories: <0 (indicating an improvement), 0-2, >2-4, and >4 (indicating worst deterioration).

Treatments

The recommended dosage for trabectedin in relapsed ovarian cancer is 1.1 mg/m² administered as a 3-hour infusion every 3 weeks (3h_q3w), immediately after infusion of 30 mg/m² PLD. There is no predefined limit as to the number of cycles of treatment with trabectedin. Treatment may continue as long as the treating physician feels there is benefit, even in the presence of apparent progression of disease. To minimize the risk of PLD infusion reactions, PLD infusion should be in accordance with the SmPC. Any

trabectedin dose modifications and/or change in dosing interval should be in accordance with the SmPC and the treating clinician's best clinical judgment.

Patients must receive corticosteroids (e.g., 20 mg dexamethasone iv) 30 minutes prior to PLD (in combination therapy) or Yondelis (in monotherapy); not only as anti-emetic prophylaxis, but also because it appears to provide hepatoprotective effects. Additional anti-emetics may be administered as needed.

1.

Trabectedin administration history will be summarized presenting the number of previous cycles received prior to IC. Descriptive statistics will be calculated for total number of cycles started or infusions received, trabectedin administration setting (inpatient/ outpatient), trabectedin administered dose per infusion (mg), cycle duration (days), trabectedin treatment duration will be presented as number of weeks on trabectedin treatment. Cumulative dose administered, dose intensity (mg)/week, relative weekly dose intensity (%), and total dose of trabectedin administered (mg) per cycles will also be presented. The number and percentage of patients with modifications (including dose missed, reductions, dose delays, or doses withheld) from the investigator reported schedule will be summarized by type of dose modification and reason for the dose modification. The number of dose missed/reductions/interruptions/delays per patient will also be summarized.

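### Best and worst performance-status scores depend on how many assessments a patient had, and no by-cycle summary is planned to describe evolution

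*SAP*

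**What the plan says.** The SAP (section 2) and the protocol (section 2.2) make the evolution of performance status a secondary objective, to be reported overall and by prior antiangiogenic use.

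The analysis is in SAP 9.4.4, with matching text in protocol 10.4.4: "ECOG/WHO performance status scores will be summarized at baseline, worst/best scores under treatment, and scores at end of treatment". The next sentence adds change scores: "The change in scores from baseline to best/worst and end of treatment scores will also be summarized presenting categories". The categories are <0, 0-2, >2-4 and >4.

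Three features of data collection matter:

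- Visit timing is not fixed. Protocol 6.2.2 states: "Subsequent visits will occur at the treating clinician's typical schedule".
- Scores are collected only where they exist: "On each subsequent visit during the Observation Period, the following data, if available, will be collected". ECOG is one of the listed items.
- Treatment length is open. SAP 3.1 states: "There is no predefined limit as to the number of cycles of treatment with trabectedin". The Observation Period ends at 12 months, or earlier if trabectedin stops, the patient leaves the study or she dies (protocol 6.2).

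ECOG is not among the follow-up data in protocol 6.3 and is not marked for follow-up in Table 1. The SAP gives no assessment window for the under-treatment or end-of-treatment score. It plans no summary by cycle or time point and no count of ECOG assessments per patient.

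**The concern.** Evolution means a course over time. The study collects a series of scores, and the plan reduces it to four values: a start, an end and two extremes.

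The extremes cause the difficulty. A minimum or maximum over many readings tends to lie further from the first reading than one over few readings, even when nothing has changed. A patient with two or three visits and a patient with a dozen are therefore not measured alike. If prior antiangiogenic use goes with shorter or longer treatment, the best-score and worst-score tables could differ between the groups for that reason alone. A reader could take this for a difference in how patients fared.

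The end-of-treatment score avoids the problem of extremes but has no common timing. Treatment may stop for progression, toxicity or completion, at a different cycle in each patient.

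**Working it through.** The documents give no figure for ECOG variability or for the expected result, so there is no planned number to reproduce. The check asks how the planned summaries behave when performance status does not truly change.

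**1. Range of visit counts.** With cycles every 3 weeks (SAP 3.1) and a 12-month Observation Period, a patient can have up to 365.25 / 21 = 17.4, so about 17, on-study cycles. A patient who stops early may have two or three.

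**2. Independent visits (illustration).** Let p be the chance at a single visit of a one-grade fluctuation in a given direction, and k the number of visits. The chance that the extreme in that direction differs from baseline is 1 − (1 − p)^k. The values of p are assumptions.

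| k | p = 0.05 | p = 0.10 |
|---|---|---|
| 4 | 1 − 0.95^4 = 18.5% | 1 − 0.90^4 = 34.4% |
| 6 | 26.5% | 46.9% |
| 12 | 46.0% | 71.8% |
| 17 | 58.2% | 83.3% |

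These figures apply to worst score above baseline. For best score below baseline they apply only to patients who start above ECOG 0.

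**3. Correlated visits.** Scores from one patient are unlikely to be independent. The second check simulated a stable underlying score with a between-patient SD of 0.8 and a within-patient SD of 0.6. It was cut into grades at 0, 1.2, 2.2 and 3.2, with 200,000 patients per setting. All of these inputs are assumptions.

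| Visit-to-visit correlation | Best below baseline, 4 → 17 visits | Worst above baseline, 4 → 17 visits |
|---|---|---|
| 0 | 35.6% → 45.5% | 44.0% → 68.6% |
| 0.5 | 30.8% → 43.8% | 36.5% → 64.0% |
| 0.9 | 17.6% → 33.8% | 18.9% → 42.5% |

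Correlation lowers the percentages, but the rise with visit count remains. The mean change from baseline to the last visit was 0.00 (to two decimals) in nearly every setting and never further from zero than 0.003. The planned end-of-treatment change therefore does not have this bias.

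**4. The change categories.** ECOG takes whole grades from 0 to 5, where 5 is death (protocol Appendix 14.2). Listing every pair of baseline and later scores gives:

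- <0: any improvement, including one grade.
- 0-2: no change, one grade worse or two grades worse.
- >2-4: three or four grades worse.
- >4: reached only by going from 0 to 5.

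The categories are asymmetric. A one-grade chance improvement in the best score is counted as improvement. A one-grade chance worsening in the worst score stays with no change. A real loss of one or two grades by end of treatment is also hidden there.

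**The case against.** The strongest reply is that the plan already holds a usable measure. Baseline and end-of-treatment scores are both summarised, and so is the change between them; that is a two-point measure of evolution without the bias of extremes. A reader might infer from the emphasis on best and worst that evolution is not measured at all. The documents do not support that.

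Four further points have force:

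- The percentages rest on assumed fluctuation rates, and the simpler formula also assumes independence.
- A one-grade worsening does not leave the 0-2 category, so the percentages for worst score apply to the score distribution and not to movement between the planned change categories.
- Nothing in the documents shows that the antiangiogenic groups will differ in time on treatment. If they do, the exposure tables by group will show it, and no test of ECOG is planned.
- Patients who stop early may have poorer performance status, which could mask or reverse the effect on the worst score. It cannot be said that longer-treated patients will look both better and worse, only that extremes tend that way with other things equal.

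Table shells are kept separately (SAP section 11) and might contain more detail, but the SAP text does not ask for it.

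All of this limits the claim without removing it. Seeing unequal exposure in another table does not tell a reader how much of a best or worst difference it explains. The end-of-treatment change remains without common timing and is reported in categories that hide moderate worsening.

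**Conclusion.** The point holds in a limited form. Best and worst ECOG scores depend on the number of assessments, and they are not comparable between antiangiogenic groups if time on treatment differs. With no true change, independent visits and a 5-10% one-grade fluctuation per visit, 19-34% of patients would differ from baseline at 4 visits and 46-72% at 12. These figures show the mechanism and do not predict this study's results; with correlated visits the effect is smaller.

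The change to end of treatment escapes this bias. On its own it is a thin answer to an objective about evolution, because of its variable timing and its 0-2 category. The endpoint is secondary and descriptive, so the primary analysis and the sample size are unaffected. This is a cheap and worthwhile improvement to the plan.

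**What to change.** In SAP 9.4.4:

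- Add, as the main description of evolution, a shift table of ECOG from baseline by cycle (for example cycles 2, 4 and 6). Use single grades, show the number still on treatment and the number assessed at each cycle, and present it overall and by prior antiangiogenic use.
- Keep the end-of-treatment change.
- Keep best and worst scores as supportive tables, and report the number of ECOG assessments per patient beside them.
- Record the addition in SAP section 10, which now reports no significant changes from the protocol's analyses.

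The cost is SAP wording and one extra table from scores already collected. Its limit is that it describes only patients still on treatment with an available score, which the two counts make visible. A time-to-sustained-deterioration analysis is not proposed: ECOG is not collected in follow-up, so worsening at the last on-treatment visit could not be confirmed.

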2.2 Secondary Objectives

The secondary objectives will be to determine the following based on real-life clinical data overall and by previous usage of antiangiogenic drug:

- Response rate (CR + PR) and DCR (CR + PR + SD)
- Overall survival (OS)
- Evolution of the patient's performance status (PS)
- Treatment duration and number of cycles, treatment exposure, and time to next treatment
- Safety of the combination of trabectedin + PLD.

Version 4- Amendement 2

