14.2 Appendix – Performance Status

Performance status evaluated according to the Eastern Cooperative Oncology Group (ECOG) score (also known as the World Health Organization [WHO] score) is shown in Table 2.

Table 2. ECOG Performance Status

Grade	ECOG Score Description*
0	Fully active, able to carry on all pre-disease performance without restriction
1	Restricted in physically strenuous activity but ambulatory and able to carry out work of a light or sedentary nature, e.g., light house work, office work
2	Ambulatory and capable of all self-care but unable to carry out any work activities. Up and about more than 50% of waking hours
3	Capable of only limited self-care, confined to bed or chair more than 50% of waking hours
4	Completely disabled. Cannot carry on any self-care. Totally confined to bed or chair
5	Dead

^{*} As published in American Journal of Clinical Oncology: Oken MM, Creech RH, Tormey DC, Horton J, Davis TE, McFadden ET, et al. Toxicity and response criteria of the Eastern Cooperative Oncology Group. *Am J Clin Oncol*. Dec 1982;5(6):649-655.

The ECOG Performance Status is in the public domain therefore available for public use. Credit is given to the Eastern Cooperative Oncology Group, Robert Comis M.D., Group Chair.

PharmaMar Page 47

Version 4- Amendement 2

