9. STATISTICAL METHODS OF ANALYSIS

9.1 General Principles

All analysis will be based on the FAS and will be presented overall and by previous antiangiogenic usage (yes/no).

Appropriate descriptive statistics will be produced for each parameter. For continuous data the mean, standard deviation, median, minimum and maximum will be presented. For categorical data, the frequency and percentage in each category will be presented. The data will be analyzed using the normal approximation and its 95% CI. However, in analyses where sample size is considered to be too low, the exact binomial estimator and its 95% CI will be calculated. Time-to-event endpoints (PFS and OS) and their fixed-time estimations will be analyzed using the Kaplan-Meier (KM) method.

Any p-values presented will be descriptive in nature and the significance level selected will be 5%.

Statistical analyses will be conducted using SAS version 9.4 or later for Windows, and/or any other applicable software suitable for the planned statistical analyses.

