11. LIST OF PLANNED TABLES AND FIGURES

Table shells corresponding to this SAP will be documented separately. The shells document will contain the details regarding the content and layout of the tables and graphs to serve as requirement documentation for statistical programming.

Unless otherwise specified, the following outputs will be produced subject to study design and the availability of data, overall and by previous antiangiogenic usage.

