11.1 Planned Tables

Category	Table Title
Disposition	Summary of Enrollment by Country and Site
Disposition	Reasons for Non-participation
Disposition	Summary of Inclusion and Exclusion Criteria
Disposition	Patient Disposition
Demographics and Baseline	Demographics and Baseline Characteristics
Demographics and Baseline	Medical History
Demographics and Baseline	Prior Anticancer Therapy
Demographics and Baseline	Baseline Imaging
Effectiveness - Primary Endpoint	Progression-free Survival
Effectiveness - Secondary Endpoint	Best Tumor Response
Effectiveness - Secondary Endpoint	Overall Survival
Effectiveness	Summary of Symptomatic Response
Other Secondary Endpoints	Summary of ECOG Performance Status
Treatments - Secondary Endpoints	Exposure to Trabectedin
Treatments - Secondary Endpoints	Trabectedin Dose Modification
Treatments - Secondary Endpoints	Exposure to PLD
Treatments - Secondary Endpoints	PLD Dose Modification
Treatments - Secondary Endpoints	Subsequent Anticancer Therapy after Stopping Trabectedin
Safety	Overall Summary of Patient Incidence of Treatment-Emergent Adverse Events
Safety	Overall Summary of Patient Incidence of

Category	Table Title
	Treatment-Emergent Adverse Drug Reactions
Safety	Treatment-Emergent Adverse Events
Safety	Treatment-Emergent Adverse Drug Reactions Related to Trabectedin
Safety	Treatment-Emergent Adverse Drug Reactions Related to PLD
Safety	Treatment-Emergent Serious Adverse Events
Safety	Treatment-Emergent Serious Adverse Drug Reactions Related to Trabectedin
Safety	Treatment-Emergent Serious Adverse Drug Reactions Related to PLD
Safety	Treatment-Emergent Adverse Events Grade 3 or Higher
Safety	Treatment-Emergent Grade 3 or Higher Adverse Drug Reactions Related to Trabectedin
Safety	Treatment-Emergent Grade 3 or Higher Adverse Drug Reactions Related to PLD
Safety	Treatment-Emergent Serious Adverse Events Grade 3 or Higher
Safety	Treatment-Emergent Grade 3 or Higher Serious Adverse Drug Reactions Related to Trabectedin
Safety	Treatment-Emergent Grade 3 or Higher Serious Adverse Drug Reactions Related to PLD
Safety	Treatment-Emergent Adverse Events in Descending Order of Frequency
Safety	Treatment-Emergent Adverse Drug Reactions Related to Trabectedin in Descending Order of

Category	Table Title
	Frequency
Safety	Treatment-Emergent Adverse Drug Reactions Related to PLD in Descending Order of Frequency
Safety	Treatment-Emergent Serious Adverse Events in Descending Order of Frequency

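### The ECOG change classes count worsening by one or two grades together with no change

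*SAP*

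**What the plan says.** Performance status is a secondary objective in both documents, to be described overall and by prior antiangiogenic use: "Evolution of the patient's performance status (PS" in protocol section 2.2 and "Determine evolution of the patient's performance status (PS" in SAP section 2.

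SAP section 9.4.4 plans two ECOG summaries. The first is of the scores themselves at baseline, best and worst on treatment, and end of treatment. The second is of within-patient change: "The change in scores from baseline to best/worst and end of treatment scores will also be summarized presenting categories", and the classes are "<0 (indicating an improvement), 0-2, >2-4, and >4 (indicating worst deterioration". Protocol section 10.4.4 has the same classes, so the two documents agree.

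Protocol appendix 14.2 gives the scale as whole grades from 0 to 5, where 5 is death. Grade 2 is described as "Ambulatory and capable of all self-care but unable to carry out any work activities".

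The general rule in SAP section 9.1 is "For continuous data the mean, standard deviation, median, minimum and maximum will be presented", with frequencies and percentages for categorical data. SAP section 11.1 lists one ECOG table, titled "Summary of ECOG Performance Status". Its content is left to a separate document: "The shells document will contain the details regarding the content and layout of the tables and graphs". That document was not available for this review.

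**The concern.** On a whole-number scale the class 0-2 contains exactly three values: no change, one grade worse and two grades worse. The classes are also lopsided. Any improvement, even of one grade, is shown separately as <0, but worsening is shown separately only from three grades upward. A move from grade 0 to 2, or from grade 2 to 4, is a large loss of function and is reported in the same row as stability.

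These classes are the only within-patient ECOG summary that the SAP text specifies. If the table is built as written, the report on a stated secondary objective will not say how many patients lost one or two grades. Two groups defined by prior antiangiogenic use could differ in such losses and still show identical class counts.

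There is a smaller point at the top of the scale. No living patient can reach the >4 class, and the documents do not say whether death is scored as grade 5.

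**Working it through.** The plan states no figure for ECOG change, so there is nothing to reproduce. The check has two steps.

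**Step 1. Which moves fall in which class.** Inputs: the grades in protocol appendix 14.2 and the classes in SAP section 9.4.4. There are 5 × 5 = 25 baseline-to-later pairs among living grades 0 to 4.

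| Class | Changes included | Number of moves |
|---|---|---|
| <0 | -4 to -1 | 10 |
| 0-2 | 0, +1, +2 | 5 + 4 + 3 = 12 |
| >2-4 | +3, +4 | 2 + 1 = 3 |
| >4 | none | 0 |

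Of the 4 + 3 + 2 + 1 = 10 worsening moves, 4 + 3 = 7 share a class with the 5 unchanged pairs. All 10 improving moves are visible. These are counts of possible moves, not of patients.

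If death were scored as 5, a death from baseline grade 0 would fall in >4, from grade 1 or 2 in >2-4, and from grade 3 or 4 in 0-2.

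**Step 2. Whether the other planned summaries recover the count.** The documents give no ECOG distribution, so the counts below are assumed; only N = 300 is the planned minimum.

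- Baseline, grades 0/1/2: 135/120/45.
- End of treatment, grades 0/1/2/3: 105/105/70/20.
- Change classes: 15 patients in <0 and 285 in 0-2.

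The sum of all changes is fixed by the score tables: (105 + 2 × 70 + 3 × 20) - (120 + 2 × 45) = 305 - 210 = 95.

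- *Fewest worsened.* The 15 improvers contribute at most -15, so the worsened patients must total at least 95 + 15 = 110 grades. None can exceed +2, so at least 110/2 = 55 worsened (18.3%). This is attained by 0→0 100, 0→2 35, 1→0 5, 1→1 95, 1→3 20, 2→1 10, 2→2 35.
- *Most worsened.* The 15 improvers contribute at least -30, since no baseline grade exceeds 2. The worsened patients then total at most 95 + 30 = 125 grades, so at most 125 worsened (41.7%). This is attained by 0→0 90, 0→1 45, 1→1 60, 1→2 60, 2→0 15, 2→2 10, 2→3 20.

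Suppose the statistics for continuous data were also reported for the change. Two data sets then agree on everything shown:

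| | Data set 1 | Data set 2 |
|---|---|---|
| Grade 0 to 0 / 1 / 2 | 93 / 0 / 42 | 90 / 24 / 21 |
| Grade 1 to 0 / 1 / 2 / 3 | 11 / 102 / 0 / 7 | 0 / 81 / 39 / 0 |
| Grade 2 to 0 / 1 / 2 / 3 | 1 / 3 / 28 / 13 | 15 / 0 / 10 / 20 |
| Sum of changes; mean | 95; +0.32 | 95; +0.32 |
| Sum of squared changes | 227 | 227 |
| Median, minimum, maximum | 0, -2, +2 | 0, -2, +2 |
| Number worsened | 42 + 7 + 13 = 62 (20.7%) | 24 + 21 + 39 + 20 = 104 (34.7%) |

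The SD is √((227 - 95²/300)/299) = 0.81 in both.

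There is one exception. If every change lies in 0-2, the sum S and the sum of squares Q determine the counts: (Q - S)/2 patients at +2 and 2S - Q at +1. Take baseline 150/120/30 at grades 0/1/2 and end of treatment 90/120/75/15 at grades 0/1/2/3. The score tables allow 75 worsened (15 at +1, 60 at +2; SD 0.81) up to 135 worsened (all at +1; SD 0.50), with mean +0.45 in both. Here the SD, if reported with the mean, would identify the number.

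**The case against.** The study is descriptive, and performance status carries no hypothesis, threshold or decision rule. The score summaries will show how the group as a whole drifts; what is lost is detail within patients. This stands, and it limits the weight of the point. It does not remove it, because within-patient change is what the classes are meant to describe.

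The table shells may list every integer change, and the SAP does not exclude a mean and SD for the change. Both are possible. But the SAP text fixes the classes, so a shell that follows it would reproduce the problem, and step 2 shows that the mean, SD, median and range do not give the count in general.

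The numerical range comes from assumed counts and extreme arrangements. In the 55-patient case every worsened patient moves exactly two grades. That is fair: the example shows that the number cannot be recovered, not how large the loss would be.

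The question of deaths is largely hypothetical. The best and worst scores are those on treatment, the schedule in protocol Table 1 has no performance status entry at follow-up, and deaths are summarised separately. An empty >4 row does no harm. One sentence in the SAP would settle it.

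**Conclusion.** The concern holds. As written, the classes show every improvement but place 7 of the 10 possible worsening moves between living grades with no change. No summary specified in the SAP text reports how many patients worsened by one or two grades.

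The class membership follows directly from the stated classes and the whole-number scale, and needs no assumption. The number of patients affected cannot be stated. The ranges of 55 to 125, and of 62 against 104, rest on assumed distributions and only demonstrate that the count is not identified. The conclusion is about the SAP text; unseen shells could already be finer. It is a weakness shared with the protocol, not a discrepancy between the two documents, and it is confined to one descriptive secondary endpoint.

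**What to change.** In SAP section 9.4.4:

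- Split the 0-2 class into 0, +1 and +2, and keep worsening of three or more grades separate. This alone would report the missing count.
- Add shift tables of baseline by worst score and baseline by end-of-treatment score, overall and by prior antiangiogenic use. They also show the grade from which patients worsened. Include a missing category and state the denominator, because scores are collected only if available.
- State whether death is scored as grade 5. If it is not, drop the >4 class.

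The protocol's classes can stay as subtotals. If they are replaced instead, record the change in SAP section 10.

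The cost is a short SAP revision and minor work on the table shell and programming. No new data are needed, since protocol sections 6.2.1 and 6.2.2 already provide for collecting the scores.
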